6.2.2 Termination of Baseline Period, Initiation of Test Period

Day 0, the following will be performed:

1. Subjects will be instructed to administer the first dose of test product prior to their mid-day meal and the second daily dose just prior to bedtime on Day 0.
2. Subjects will be instructed to keep their Dexcom CLARITY app active, so that glucose monitoring data can be accessed by the study team.
3. Subjects will be reminded to mail/email diary cards to the study team every 7 to 10 days. Subjects using an insulin pump, will be advised to mail/email a copy of their pump settings and insulin doses every 7 to 10 days or upload their pump data to a prespecified, linked online account compatible with their pump (i.e. Medtronic CareLink, Tandem T Connect or Glooko), whereby the relevant data can be abstracted by the study team.
4. Subjects will also be instructed not to make any modifications to their diet or exercise routine.
5. Subjects will be scheduled to return to the OPC for Visit 2 and instructed to return all unused tablets in the original container(s) along with any diary cards.

On Day 48 (Visit 2, Final Visit):

1. Subjects will report to the OPC in the morning, before 12:00 noon. If a subject is not able to comply with the Day 0 requirement, a variance of -2 days (or Day 46 or 50) is allowed.
2. Urine pregnancy test will be obtained for females of childbearing potential.
3. Subjects will return all unused tablets in the original container(s) along with any diaries.
4. Blood pressure, height, weight, and waist and hip circumference will be obtained to calculate the WHR. Fasting samples will be obtained for glucose and triglycerides. Additional blood samples will be obtained for HbA1c, routine hematology, routine chemistry assessments CPR, and for exploratory biomarkers hs-CRP and 1,5AG.
5. An abbreviated physical exam will be performed.
6. Study staff will review the subject's diary in order to reconcile tablets returned with any doses missed.

7. Subjects will be questioned about any changes in health status/adverse events and any changes in therapy or medications
8. Study personnel will remove the CGM sensor from the subject's abdomen and download the data to the Dexcom CLARITY data storage location.

7. SAFETY AND EFFICACY EVALUATIONS

7.1 Vital Sign Measurements

Single measurements of blood pressure and heart rate will be measured, with subjects in a seated position, at the start of every visit.

7.2 Tests for Safety Assessments

Hematology (CBC), and chemistry testing and CPR, will be performed at Screening (Visit 1) to determine eligibility and at the completion of the Test Period (Visit 2) to evaluate changes in lab values. The complete list of hematology and chemistry laboratory safety parameters to be collected is provided in [Appendix 2](#); See [Table 3](#) and [Table 4](#).

A urine pregnancy test will be performed on women of child-bearing potential at screening to determine eligibility (pregnant women are not eligible) and at all subsequent Visits. Women who become pregnant at any time during the study should be discontinued at the investigator's discretion and all pregnancies need to be followed to document the outcome of the pregnancy.

In addition to the results of the urine pregnancy tests performed on women of child-bearing potential, study personnel will enter all laboratory data into the Electronic Case Report Form (eCRF).

Blood and urine samples will be collected, processed, and stored according to Mayo Clinic's established procedures.

All laboratory testing, except the 1,5-Anhydroglucitol (1,5-AG) samples will be tested at Mayo Clinic. The 1,5-AG samples will be tested by LabCorp.

All Mayo Clinic analytical testing will be performed by validated/established Mayo Clinic test methods or by methods routinely performed in the Mayo Clinic Core Laboratory.

Analytical testing performed at LabCorp will be performed by validated/established LabCorp test method.

7.3 Tests for Efficacy Assessments

7.3.1 Primary Efficacy Assessments

For the primary efficacy endpoint, HWR (Hip-to-Waist Ratio) and blood pressure will be measured at Day -28, Day 48 and used, along with HbA1c, to calculate the eGDR (estimated Glucose Disposal Rate) (WilliamsKV-ref 34).

7.3.2 Secondary and Exploratory Efficacy Assessments

Secondary and exploratory evaluations will also be performed. The specific evaluations and sample collection and analysis time points are listed in [Table 3](#), [Appendix 2](#).

Secondary efficacy evaluations require measurement of glucose variability, insulin usage, and triglycerides. Study personnel will enter the results into the eCRF.

For the secondary endpoint of glucose variability, Dexcom CGM sensors will be supplied by BioKier and used to record continuous glucose levels every 5 minutes during the study.

The CGM sensor is water-resistant and **must** be applied to the subject's abdomen. The CGM sensor is held in place with a self-adhesive pad and requires no subject interaction with the device or the need for calibration.

The CGM continuously measures glucose in interstitial fluid through a small (5mm long, 0.4mm wide) filament that is inserted just under the skin. It records glucose levels every 5 minutes, capturing up to 2880 glucose results for up to 10 days. Subjects will be instructed to keep their Dexcom CLARITY app active, so that glucose monitoring data can be accessed by the study team throughout the study. When the subject returns to the OPC at Visit 2, the CGM sensor will be removed by study staff and the data stored on the sensor will be retrieved by the reader and downloaded to the Dexcom CLARITY data storage location. The data will then be accessed by Mayo personnel and authorized BioKier personnel, including the statistician.

The other secondary efficacy endpoint, triglycerides, will be measured in blood samples from Visits 1, and 2 by the Mayo Clinic Laboratory.

Exploratory evaluations require analysis of the laboratory tests for hsCRP and 1,5-AG, from samples obtained Visits 1 and 2.

All blood samples for exploratory evaluations will be collected and will be processed according to Mayo Clinic's established procedures. All analytical testing will be performed on the secondary

and exploratory endpoints by validated/established Mayo Clinic test methods or by methods routinely performed in the Mayo Clinic Core Laboratory.

Study personnel will enter the exploratory test results into the eCRF.

7.4 Adverse Events

An adverse event is defined as any untoward medical occurrence that occurs during a clinical trial, whether or not considered related to the participation in the study or the test product received. Collection of adverse events in this study will begin at the time of administration of a subject's first dose of test product. Any untoward events that may occur between the screening visit and the first dose of test product should be recorded as medical history.

An adverse event or suspected adverse reaction is considered "serious" if, in the view of either the investigator or sponsor, it results in any of the following outcomes:

- Death
- Life-threatening
- Inpatient hospitalization or prolongation of existing hospitalization
- Persistent or significant incapacity or substantial disruption of the ability to conduct normal life functions, or
- Congenital anomaly/birth defect

Important medical events that may not result in death, be life-threatening, or require hospitalization may be considered serious when, based upon appropriate medical judgment, they may jeopardize the subject and may require medical or surgical intervention to prevent one of the outcomes listed in this definition. Examples of such medical events include allergic bronchospasm requiring intensive treatment in an emergency room or at home, blood dyscrasias or convulsions that do not result in inpatient hospitalization, or the development of drug dependency or drug abuse.

An adverse event or suspected adverse reaction is considered "life-threatening" if, in the view of either the investigator or sponsor, its occurrence places the subject at immediate risk of death. It does not include an adverse event or suspected adverse reaction that, had it occurred in a more severe form, might have caused death.

Suspected adverse reaction means any adverse event for which there is a reasonable possibility that the test product caused the adverse event. For the purposes of expedited safety reporting, "reasonable possibility" means there is evidence to suggest a causal relationship between the test product and the adverse event.

Subjects will be observed and questioned at every visit for the possible occurrence of adverse experiences; diaries will be reviewed to determine if any adverse experiences occurred between visits. Subjects should be asked to contact the investigator or study staff on any day on which an untoward event is experienced, whether the subject feels it is related to the test product or not.

All adverse experiences, whether observed by the investigator or study staff, or reported by the subject, will be recorded in the subject's study file and entered into the clinical database and will include the date of onset, outcome, date of resolution (if applicable), maximum severity, action taken, and relationship to the test product. Whenever possible, a diagnosis will be assigned rather than the constellation of symptoms.

Medical history/current medical conditions and adverse events will be coded using the medical dictionary (MedDRA) terminology.

8. PROVISIONS TO MONITOR DATA TO ENSURE SUBJECT SAFETY

The study protocol defines eligibility criteria designed to exclude patients for whom participation could pose unacceptable risks. Numerous medical assessments and laboratory tests throughout the study allow for continuous monitoring of safety. The Mayo Clinic Principal Investigator (PI) will review all lab work and adverse events. All adverse events will be reported to BioKier and the Mayo Clinic IRB in accordance with the Mayo Clinic IRB requirements.

9. DISCONTINUATION OF A STUDY PARTICIPANT

9.1 Screen Failures

A subject is considered a screen failure if he/she does not meet the inclusion/exclusion criteria or does not go on to receive test product for any reason.

9.2 Reasons for Discontinuation

A subject will be discontinued from the study for any of the following reasons:

1. Withdrawal of consent
2. Hospitalization
3. Treatment of an adverse event requires that the investigator be informed of the test product to which the subject was assigned
4. Death
5. Lost to follow-up
6. Sponsor or investigator requests discontinuation of a subject for safety reasons
7. Subject requires or has taken a prohibited medication for an extended period of time

8. Significant and/or persistent vomiting or diarrhea for an extended period of time, and vomiting/diarrhea can impact dosing/gut motility
9. Subject is non-compliant with any of the other requirements of the study

The reason for discontinuation will be documented in the subject's study record and relevant page of the eCRF.

For all subjects discontinuing before completing all study procedures and test visits, study personnel should perform a termination visit. At this visit subjects should return all unused test product and diary cards, vital signs should be obtained, and chemistry and hematology samples collected and tested. Additionally, if the subject is a woman of child-bearing potential, a urine pregnancy test should be performed.

If the subject is unable or unwilling to come to the clinical site for a termination visit, study personnel should conduct a follow-up telephone call to assess the reason for the subject's withdrawal from the study and to arrange for the return of unused test product.

For subjects lost to follow up, every effort should be made, including sending a certified letter, to contact the subject to come to the clinical site for termination visit procedures and to return test product.

10. DATA REVIEW AND DATABASE MANAGEMENT

10.1 Data Collection

All data should be recorded, handled, and stored at Mayo Clinic in a way that allows its accurate reporting and interpretation.

Only specified study data and laboratory tests performed by Mayo Clinic will be entered into an eCRF. All data captured for this study must have an external originating source (either written or electronic); the eCRF is not considered as source.

The investigator must maintain source documents for each study subject, which consist of ICFs, case and visit notes (e.g., clinic medical records) containing demographic and medical information, laboratory data, diary card data, and the results of any other tests or assessments. All data must be traceable to these source documents. The investigator must also keep the original ICF signed and dated by the subject (a signed copy is given to the subject).

CGM data will be collected using the Dexcom G6 device. Data will be downloaded from the Dexcom G6 sensor to the Dexcom CLARITY data storage location in a manner that will allow accurate reporting and interpretation by the study team.

10.2 Database Management and Quality Control

The study database consists of data from the eCRF database, and data retrieved from the CGM sensors used during the study.

Study staff will enter required data into the eCRF on an ongoing basis as data are collected throughout the study. Automatic validation programs check for data discrepancies and generate appropriate error messages. Additionally, manual data queries will require resolution by the study personnel before query close-out. The eCRF will be accessible to authorized personnel only, and the system will be secured to prevent unauthorized access to the data and the system. This includes the requirement for a user ID and password to enter or change data. The level of access to the eCRF system (e.g., data entry, view rights only) will be dependent on each person's role in the study. The investigator will be required to certify (via electronic signature) that the data entered in the eCRF are complete and accurate.

Mayo Clinic personnel will review all data (eCRF) for completeness and accuracy and issue data queries about any inconsistent, incorrect or missing data. Once all queries have been resolved and the database is declared to be complete and accurate, it will be locked. After database lock, BioKier will provide the investigator with electronic media containing of all clinical study data for archiving.

10.3 Subject Confidentiality

In order to maintain subject confidentiality, only a subject number will be used to identify study subjects. Initials should not be used or referred to in any written communications.

The investigator is expected to comply with all applicable privacy regulations such as the Health Insurance Portability and Accountability Act (HIPAA) of 1996.

11. DATA ANALYSIS

Analysis of the data will be conducted under the direction of BioKier personnel in compliance with the Statistical Analysis Plan (SAP) and internal guidance documents and industry standards.

11.1 Objectives and Endpoints

11.1.1 Analysis Objectives

To evaluate the effects of BKR-017 tablets (active test product) when administered orally to T1D patients twice daily. Active test product will be administered for a 7 -week period.

11.1.2 Primary Efficacy Endpoint

The primary efficacy endpoint is the comparison of insulin sensitivity, calculated as the eGDR³⁴ on Days -28, and 48.

11.1.3 Secondary Efficacy Endpoints

Secondary endpoints include:

1. Glucose variability (from CGM data)
2. Fasting triglycerides
3. Insulin usage (from diary card)

11.1.4 Safety Endpoints

A descriptive assessment of safety will be made using vital signs, and selected chemistry assessments including bilirubin, alkaline phosphatase (ALP), aspartate aminotransferase (AST), alanine aminotransferase (ALT), blood urea nitrogen (BUN), and creatinine.

Additionally, clinically significant changes in the Visit 1 and 2 laboratory values obtained from routine hematology and chemistry (including CPR) testing will be reported in the eCRF along with adverse events reported during the test product administration period.

Adverse events reported during the study will be attributed to the test product administered at the time the event occurred.

11.1.5 Exploratory Endpoints

The exploratory endpoints include changes in measurements of hsCRP and 1,5-AG.

11.2 Sample Size

Differences in eGDR (mg/kg/min) between Days -28, and 48 will be assessed by calculating eGDR from HWR (Hip-to-Waist Ratio), blood pressure, and HbA1c, off treatment and on treatment. for each subject. Statistical significance will be assessed by comparing eGDR at each of Day -28 and Day 48 to eGDR at Day -28 (i.e., baseline) with a paired t-test.

This study of 12 subjects is considered large enough to draw some preliminary clinical conclusions.

12. ANALYSIS CONVENTIONS

12.1 Analysis Sets

An analysis database of all efficacy data collected will be generated (ITT Population). In addition, an analysis set of all subjects without major protocol violations (per protocol population) will consist of all subjects who took at least 85% of the 96 required doses (i.e., 82 or more doses).

The safety analysis set will include all subjects who received any amount of test product.

Analysis plans are detailed further in a Statistical Analysis Plan document (SAP).

12.2 Missing Data

All missing data will remain missing. No values will be imputed.

12.3 Pharmacy Records

Mayo Clinic pharmacy study records will be made available to BioKier since BioKier is supplying the test product.

Inventory or dispensing records maintained by the Mayo Clinic pharmacy that identify the quantity of active test product that has been dispensed to a given subject will be reviewed.

12.4 Demographics and Baseline Characteristics

All data for background and demographic variables will be listed and summarized by subject. Relevant medical history, current medical conditions (including hypertension category (Y/N), results of laboratory screens, and any other relevant information will be listed. No statistical inference will be performed on these data.

12.5 Subject Disposition

The number and percentage of subjects in each analysis set who complete the study or discontinue early and the reasons for discontinuation will be summarized. No statistical testing will be performed.

12.6 Efficacy Analysis

All efficacy analyses will be repeated for both the ITT Population and the Per-Protocol Population.

12.6.1 Primary Efficacy Analysis

Differences in eGDR (mg/kg/min) between Days -28, and 48 will be assessed by calculating eGDR on Days -28, and 48 for each subject. Statistical significance will be assessed by separate within-subject comparisons of eGDR at each of Day -28, and Day 56 to eGDR at Day -28 (i.e., baseline) with paired t-tests.

12.6.2 Secondary Efficacy Analysis

Blood glucose variability will be calculated for each subject, for each 24-hour day (midnight to midnight) during which a CGM device recording is available for the entire 24-hour period. Results will be presented graphically for each subject by study day.

Triglyceride changes at Day -28 and Day 48 will be summarized as change from baseline where Day -28 is considered baseline.

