Sponsor: Mayo Clinic	Investigator:	[name]

After signing consent and meeting all inclusion criteria, subjects will be instructed on, and supplied with a study provided Dexcom G6 sensors , to collect glucose data. Subjects will be instructed to keep their Dexcom CLARITY app active, so that glucose monitoring data can be accessed by the study team throughout the study. Diary cards will be provided for the subject to record insulin doses, changes to concomitant medications and adverse events. Diary cards will be mailed/emailed to the study team every 7 to10 days throughout the study. Subjects using an insulin pump, will be advised to mail/email a copy of their pump settings and insulin doses every 7 to10 days or upload their pump data to a prespecified, linked online account compatible with their pump (i.e. Medtronic CareLink, Tandem T Connect or Glooko), whereby the relevant data can be abstracted by the study team.
 
An eight-week supply of investigational product (BKR-017) will be provided to subjects. Subjects will not start dosing until Day 0.
 
During the entire study, subjects will be asked to maintain their daily routines, including diet and exercise. Females of childbearing potential and able to become pregnant, must agree to use one of the birth control methods listed in the consent form, for the duration of the study.
 
Treatment Period: Day 0 to Day 48:
 
Day 0 will occur approximately 28 days after the screen visit (agreed upon with the subject). The study team will communicate with the subject via a phone call or virtual visit on this day. After ensuring that the CGM data collected is acceptable, subjects will be instructed to commence taking the investigational product (BKR-017) as instructed.
 
Subjects will be instructed to keep their Dexcom CLARITY app active, so that glucose monitoring data can be accessed by the study team. Subjects will continue to fill out diary cards, to record insulin doses, changes to concomitant medications and adverse events. Diary cards will be mailed/emailed to the study team every 7 to 10 days. Subjects using an insulin pump, will be advised to mail/email a copy of their pump settings and insulin doses every 7 to 10 days or upload their pump data to a prespecified, linked online account compatible with their pump (i.e., Medtronic CareLink, Tandem T Connect or Glooko), whereby the relevant data can be abstracted by the study team.
 
Subjects will be contacted by the study team on Days 18 and 28, to assess study compliance, review concomitant meds and adverse events.
 
Final Visit (Day 48):
 
At the final study visit, Visit 2 (Day 48), fasting samples (10-hour fast) will be obtained for glucose and triglycerides. Additional blood samples will be obtained for HbA1c, routine hematology, routine chemistry assessments, CPR, and the exploratory tests 1,5 AG and hs-CRP. Blood pressure, height, weight, waist and hip circumference to calculate HWR, be obtained and an abbreviated physical exam will be performed. A urine
		

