Subjects currently taking the following therapies are excluded: GLP-1 receptor agonists (e.g., Byetta®, Bydureon®, Adlyxin®, Victoza®, Saxenda®, Trulicity®, Tanzeum®, Ozempic®), Amylin analogs (e.g., Symlin®), Thiazolidinediones (e.g., Actos®, Avandia®) and any combination of these medications (e.g., Avandamet®, Avandaryl®, Duetact®, Actoplus Met®, PioMet®), Acarbose (Glucobay®), Miglitol (Glyset®). Additionally, subjects taking oral and injectable corticosteroids (e.g., prednisone), oral and injectable antibiotics, opioids and probiotics or other medications that alter gastrointestinal motility, chemotherapy, radiation, cytotoxic therapy, immune suppressants, antiepileptic drugs, colesevelam (Welchol®), and other supplements containing butyrate are also excluded from the study.			
Efficacy and Safety Evaluations			
Primary	Insulin sensitivity, as measured by the estimated glucose disposal rate (eGDR), a validated clinical tool for estimating insulin sensitivity in T1D		
Secondary	The following secondary evaluations will be performed: 1. Glucose variability 2. Triglycerides 3. Insulin usage, as reported on diary card		
Safety	Blood pressure, physical exam, chemistry, hematology and treatment-emergent adverse events		
Exploratory	1,5 AG and hs-CRP		

CLINICAL PROTOCOL SYNOPSIS		Protocol No.:	CL-301
Sponsor: Mayo Clinic		Investigator: [name]	
Statistical Analysis of Primary Endpoint:	Primary and Secondary Efficacy Data: The primary endpoint is the change from baseline (Day 0) to Day 48 in insulin sensitivity as measured by eGDR. The secondary endpoint of glucose variability (as measured from CGM data) is also the change from baseline (Day 0) to Day 24 and Day 48. However, the secondary endpoint of lowering of triglycerides measurements will be calculated from the baseline at Day -28.		
	Safety Data: Assessment of safety will be made using the change from baseline in vital signs, physical exam, chemistry, hematology, and treatment-emergent adverse events. The safety analysis set will include all Subjects that received any amount of study treatment. The safety analysis set will include all Subjects that received any amount of study treatment.		
	Sample Size Estimates: Sample size estimates are based on practical considerations.		
Synopsis Date: July 18, 2022, Amendment 2, Version 3.0			

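### Glucose variability cannot be computed at Day 48 for an on-time visit, its Day 0 baseline straddles the first doses, and Section 12.6.2 gives no estimate for it and no method for insulin usage

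*Combined protocol and SAP*

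**What the plan says.** The synopsis, under Primary and Secondary Efficacy Data, states that glucose variability from CGM "is also the change from baseline (Day 0) to Day 24 and Day 48". The Design paragraph of the same synopsis says that insulin sensitivity, insulin usage, variability and triglycerides after 7 weeks are compared with Day -28.

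Section 12.6.2 calculates variability "for each 24-hour day (midnight to midnight) during which a CGM device recording is available for the entire 24-hour period". The output is then: "Results will be presented graphically for each subject by study day". No variability metric, change score, summary statistic or test is named. Triglycerides get a change from Day -28 in the same section, and the exploratory markers get paired t-tests in Section 12.6.3.

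Section 6.2.2 tells subjects to "administer the first dose of test product prior to their mid-day meal and the second daily dose just prior to bedtime on Day 0". For Visit 2 on Day 48 it has them arrive in the morning, before noon, and at that visit "Study personnel will remove the CGM sensor from" the subject's abdomen. Section 6.2 allows visits to move by 2 days either way.

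Insulin usage is a secondary endpoint in the synopsis and in Section 11.1.3. Section 12.6.2 does not mention it. Sections 11 and 12.1 refer to a SAP for further detail.

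**The concern.** The endpoint definition, the rule for a usable day and the visit schedule do not fit together. Followed literally, they leave one of the two planned change scores empty for every subject who attends on schedule, and they measure the other from a day that is partly on treatment.

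What remains is a set of individual plots. Section 1 expects lower variability and lower insulin use, and says that clinical outcome data are needed to support claims for the product. With no metric, window or contrast fixed in advance, the choice of days and of variability measure would be made with the curves in view.

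The insulin gap matters for reading the primary result. eGDR is built from HbA1c, blood pressure and hip-to-waist ratio (Sections 7.3.1 and 11.2), with no insulin term. In a single-arm study, a reader who sees eGDR change alongside HbA1c will want to know whether insulin dose changed too, and the analysis section does not say how that will be shown.

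**Working it through.** **1. Readings in a full day.** Section 7.3.2 gives one reading every 5 minutes and up to 2880 readings in 10 days. 24 × 60 / 5 = 288 per day, and 288 × 10 = 2880, so the plan's figure is reproduced.

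**2. Each candidate day against the full-day rule.**

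| Day | Schedule | Full-day recording? |
|---|---|---|
| Day -28 | Study sensors first supplied at a visit held before midday | Doubtful |
| Day 0 | Phone or virtual contact, no sensor removal | Yes |
| Day 24 | Mid-wear, no visit | Yes |
| Day 48 | Arrival before noon, sensor removed | No, if Visit 2 is on Day 46, 47 or 48; yes, if on Day 49 or 50 |

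For Day 48, removal at noon leaves 12 × 60 / 5 = 144 of 288 readings (50%). A somewhat later removal changes the count but not the result. The two Yes entries assume that no sensor change or signal gap falls on that day.

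**3. Day 0 as baseline.** CGM is "used to record continuous glucose levels every 5 minutes during the study", and the app is kept active "so that glucose monitoring data can be accessed by the study team throughout the study", so Day 0 passes the rule. Its first dose comes before the mid-day meal and its second before bedtime. Roughly half the day (144 readings to noon) is untreated and the rest is not.

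**4. Days available instead.** With Visit 2 on Day 48, complete days can run from Day -27 to Day -1 (27 days) and from Day 1 to Day 47 (47 days). Assume that sensors are changed every 10 days from Day -28 and that change days are incomplete. Changes then fall on Days -18, -8, 2, 12, 22, 32 and 42, leaving 27 - 2 = 25 and 47 - 5 = 42 days. In Days -14 to -1 one day is lost (Day -8), and in Days 34 to 47 one day (Day 42), so each window keeps 13 of 14.

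**5. Precision of single days against 14-day means.** The plan gives no SD, so these figures are illustrative. Assume a day-to-day SD of 8 CV points, and take n = 13 from Section 4.1.

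- Single days: SE = √(2 × 64 / 13) = 3.14.
- 14-day means, independent days: SE = √(2 × 64 / 14 / 13) = 0.84.
- Ratio = √14 = 3.74. With lag-1 correlation 0.2 it is 3.10; with 0.4 it is 2.54. The ratio depends neither on n nor on the SD of 8.

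This counts day-to-day noise only. Averaging does not shrink real differences between subjects in their change. Adding a true-change SD, with independent days:

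- SD 4: √[(16 + 128) / (16 + 128/14)] = √(144 / 25.14) = 2.39.
- SD 8: √[(64 + 128) / (64 + 128/14)] = √(192 / 73.14) = 1.62.

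**6. How strict the full-day rule is.** If one lost reading voids a day and losses are independent, the share of days kept is (1 - p)^288: 0.750, 0.236 and 0.055 for p = 0.1%, 0.5% and 1%. Real gaps cluster, which would keep more days, and the rule might be applied less literally. The figures show only that the wording needs a tolerance.

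**The case against.** The single-day anchors stand only in the synopsis, which is dated as Amendment 2, Version 3.0, while the protocol is at Amendment 5, Version 6. Sections 11.1.3 and 12.6.2 name no anchor day, and 12.6.2 computes variability for every complete day. On that view the body wastes no data and the synopsis is merely out of date. This stands in part: the loss from single-day values belongs to the synopsis wording. But the synopsis is part of the current document, and the body supplies no contrast in its place.

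A separate SAP may hold the missing metric and test. None could be checked beyond the text supplied. If it does, the omissions fall away, but the Day 48 conflict stays until one passage gives way.

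Several stronger readings are tempting and are not supported:

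- That neither anchor day has a usable recording. Day 0 does; its defect is the mix of untreated and treated hours.
- That the endpoint cannot be computed at all. The Day 0 to Day 24 change can be, and Day 48 is usable if the visit slips to Day 49 or 50.
- That insulin usage has no comparison anywhere. The synopsis states one with Day -28; the measure, window, summary and test are missing. Since diary cards are first handed out on Day -28, a single-day diary baseline there is itself doubtful.
- That a rise in eGDR should count as better sensitivity only if insulin dose did not rise. The documents cite the eGDR equation without giving it, so the size and direction of any HbA1c effect cannot be worked out from them. Such a rule would also let a noisy secondary measure govern the primary at n = 13.

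Finally, this is a secondary endpoint in a small study that Section 11.2 says is meant for preliminary conclusions. That limits the severity.

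**Conclusion.** The point holds. Under the plan's own rules, an on-time completer has no Day 48 variability value. This needs no assumption beyond the visit schedule and the full-day rule. The Day 0 baseline is recorded but partly treated, and it conflicts with the Day -28 comparator elsewhere in the synopsis. In the text supplied, Section 12.6.2 gives no estimate for variability and no method for insulin usage.

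The gain from multi-day means is less certain. It is up to about 2.5 to 3.7 fold in standard error for day-to-day noise alone, under an assumed lag-1 correlation of 0.4 to 0. It is about 1.6 to 2.4 fold if true changes have an assumed SD of 8 to 4 CV points, with a day-to-day SD of 8 and independent days.

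Severity: should be fixed before analysis. The primary comparison does not use CGM or insulin data and is unaffected.

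**What to change.** Reconcile the synopsis Design paragraph, the synopsis endpoint paragraph and Section 12.6.2 on the baseline and the time points. Then in Section 12.6.2:

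- Name one variability metric, for example daily CV.
- Compare its mean over Days -14 to -1 with its mean over the last 14 full days before Visit 2 (Days 34 to 47 if on time). Add a midpoint window ending on Day 24 (Days 11 to 24). Report paired differences with 95% CIs and keep the individual plots.
- Set a minimum-data rule per day, for example 70% of 288 = 201.6, so at least 202 readings. Repeat with complete days only as a sensitivity analysis.
- Summarise mean daily insulin dose over the same pre-dose and end-of-treatment windows, with the unit stated. Report it beside eGDR as context, not as a condition on the primary conclusion.

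The metric, the 14-day length and the 70% threshold are reasonable choices, not values taken from the plan; what matters is that they are fixed before the data are examined. The cost is wording and modest programming on data already collected, with no new procedure or visit. The downside is that some days with gaps enter the main analysis, which the complete-day sensitivity analysis addresses.
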